## 6.0 Study Procedures

For patients assigned to the study arm, the surgeon will use the PTeye as an intraoperative tool to identify if a suspect tissue is a parathyroid or not, during the parathyroid surgery. The surgeon will first take 5 baseline NIRAF measurements on the thyroid gland (or neck muscle, if thyroid is absent) using the disposable sterile fiber probe that is connected to the PTeye console (see Figure 1), as per device functionality requirements. The subsequent step would involve touching the target tissue in the neck with the fiber optic probe, following which the PTeye will indicate to the surgeon if the tissue is parathyroid or not. Parameters which are displayed on the PTeye console – Baseline values, Detection Intensity, Parathyroid Detection Ratio – will be recorded for each patient enrolled in the study arm. PTeye indicates that a tissue is parathyroid if it displays the 'Parathyroid Detection Ratio' is greater than 1.2. The rest of the surgical procedure will follow according to standard protocol.

For patients assigned to the control arm, the surgeon will not use the PTeye and will proceed with the parathyroid surgery as usual, while relying solely on her/his surgical experience in identifying the parathyroid glands during the operations.

**Figure 1.** A commercial fiber probe-based system (PTeye, AiBiomed) for detecting near infrared autofluorescence (NIRAF) utilized for intraoperative parathyroid gland identification. PTeye consists of 1) the console that has a display and indicates to the surgeon if a tissue is parathyroid or not, 2) a detachable fiber optic probe, and 3) a foot-pedal which is activated by the surgeon for tissue NIRAF measurements.

De-identified information regarding (i) patient demographics, (ii) duration of surgery, (iii) number of frozen section analysis performed, (iv) frozen section and permanent histology reports of all excised tissues, (v) blood calcium levels (before surgery, 5-14 days after

surgery and 6 months after surgery), (vi) parathyroid hormone (PTH) levels (5-14 days after surgery and 6 months after surgery) and (vii) postsurgical complications, if any and history of ER visits or hospitalization or repeat surgeries due to high calcium, will be compiled for all enrolled patients. These parameters would then be compared between the study arm and the control arm to truly gauge the impact or value of a device like PTeye for parathyroid surgeries.

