## **2.0 Rationale and Specific Aims**

The goal of this study is to assess whether using PTeye – a NIRAF detection modality – can improve patient outcomes and reduce healthcare associated costs after parathyroid surgeries. The specific aims of this study is to determine if PTeye is beneficial or not for (i) intraoperative identification of parathyroid tissues, (ii) improving efficiency of parathyroid surgeries, and (iii) minimizing risk of postsurgical complications.

By being able to quickly and definitively locate parathyroid glands while in the operating room, the duration of surgical procedure could be further reduced. In addition, the number of frozen section biopsy and associated costs can be minimized. Furthermore, repeat surgeries as a result of missing a diseased parathyroid gland at the time of the initial parathyroidectomy for hyperparathyroidism could potentially be avoided.

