## **10.0 Statistical Considerations**

Benmiloud *et al.* studied the impact of NIRAF-based identification of parathyroid glands which comprised of a group of 93 patients where NIRAF was used by a surgeon for parathyroid identification and a control group of 153 patients where NIRAF was not used (19). Their study reported that mean parathyroid glands identified by surgeon with NIRAF imaging was significantly higher at  $3.1 \pm 0.9$ , while that of same surgeon without NIRAF imaging was  $2.6 \pm 0.1$  ( $p=0.0001$ ). Based on this data (mean difference: 0.5 and standard deviation: 1.0), it was determined that in order to observe a statistically significant difference (i.e. for an expected mean difference: 0.7 and expected standard deviation: 1.0), 33 patients would be required per group (for a 95% powered study). Since this study may involve patient follow-up for data up to 6 months after surgery, we will thus assume an approximate data attrition rate of 20%, thus requiring a recruitment of 40 patients per group. In order to detect a difference among individual surgeons, this will require recruitment of 40 patients per arm, per surgeon. Therefore, a total of 160 patients (study and control arm) should be recruited for this study at this study site.

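### The sample size rests on the number of parathyroid glands identified, but that count is not among the items listed for collection and comparison in both arms, and no common counting rule is stated

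*Combined protocol and SAP*

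**What the plan says.** Section 10.0 takes its planning data from a cited study in which "mean parathyroid glands identified by surgeon with NIRAF imaging was significantly higher" (3.1 against 2.6 without imaging). It plans for a difference of 0.7 glands with a standard deviation of 1.0. From this it obtains 33 patients per group, and 40 after allowing for attrition. To look at surgeons individually, "this will require recruitment of 40 patients per arm, per surgeon", which brings the total to 160. No other outcome is used to justify the size.

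Section 2.0 gives the first aim as to "determine if PTeye is beneficial or not for (i) intraoperative identification of parathyroid tissues".

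Section 6.0 sets out what is compiled for all enrolled patients. The list begins "De-identified information regarding (i) patient demographics, (ii) duration of surgery, (iii) number of frozen section analysis performed" and continues with "frozen section and permanent histology reports of all excised tissues", blood calcium, parathyroid hormone, and finally complications together with emergency visits, admissions or repeat operations for high calcium. The next sentence reads: "These parameters would then be compared between the study arm and the control arm". The same section says that the PTeye console parameters "will be recorded for each patient enrolled in the study arm".

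**The concern.** A sample size calculation is useful only if the trial measures, in both arms, the variable on which the calculation was done. Here that variable does not appear in the numbered list of data to be compiled and compared, and nothing says what makes a gland identified, who counts it, or when.

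A gland that the surgeon recognises and leaves in place produces no specimen. Unless it is recorded at the operation, it cannot be reliably counted afterwards. If the omission is noticed only at analysis, the count would have to be rebuilt from whatever the operative records happen to contain, with no agreed rule. The hypothesis behind the 160 patients might then not be testable at all.

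**Working it through.** **Step 1. Confirm which variable the sample size uses.** The inputs in Section 10.0 are a difference of 0.7 glands, a standard deviation of 1.0 and stated power of 95%. Significance level and sidedness are not stated; I assumed 0.05, two-sided. The normal-approximation formula per group is n = 2(z_alpha + z_power)² × SD² / difference².

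- At 80% power: 2 × (1.960 + 0.842)² × 1.0² / 0.7² = 32.0, rounded up to 33. A t-test calculation also gives about 33.0.
- At 95% power: 2 × (1.960 + 1.645)² × 1.0² / 0.7² = 53.0, rounded up to 54. A t-test calculation gives about 54.0.
- Attrition: 33 × 1.20 = 39.6, rounded up to the stated 40. Dividing instead, 33 / (1 − 0.20) = 41.25, gives 42.
- Total: 40 per arm × 2 arms = 80 per surgeon, and 160 / 80 = 2 surgeons, a number implied but not stated.

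The stated 33 therefore goes with 80% power and not 95%. That is a separate matter and does not affect this point. What matters here is that the whole chain, 33 to 40 to 160, is calculated on glands identified per patient and on nothing else.

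**Step 2. Compare that variable with the data listed in Section 6.0.**

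| Item | Both arms? | Can it give the number of glands identified? |
|---|---|---|
| (i) Demographics | Yes | No |
| (ii) Operating time | Yes | No |
| (iii) Number of frozen sections | Yes | No. It counts tests, not glands |
| (iv) Histology of excised tissue | Yes | In part. It shows parathyroid tissue that was removed, not glands seen and left in place |
| (v) Calcium | Yes | No |
| (vi) Parathyroid hormone | Yes | No |
| (vii) Complications, emergency visits, admissions, repeat surgery | Yes | No |
| PTeye console readings (outside the numbered list) | Study arm only | No value for the control arm |

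No row gives the count in both arms.

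**Step 3. Look for the count or a definition elsewhere.** Section 2.0 names identification as an aim without a measure. Section 10.0 reports the cited study's means but gives no counting rule for this trial. Section 12.0 says that paper records, record sheets, laboratory results and histopathology are kept, but mentions neither a gland count nor a way to derive one.

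**The case against.** The strongest reply is that the Section 6.0 list need not be complete. Section 12.0 retains record sheets and medication history, and medication history is not among the seven items, so the trial evidently keeps more than the list names. Surgeons may also note the glands they see as a matter of routine. This weakens any step from *not listed* to *will not be collected*. It does not close the gap: Section 12.0 concerns retention and names no gland count, and routine notes without a shared rule are not a defined outcome.

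A second reply is that the outcome may be named in the title pages or in the study schema shown in the contents, neither of which is in the text reviewed. That is fair, and I do not claim that the trial has no named primary outcome. Even if it is named there, the Section 6.0 list and its comparison sentence would still need to be brought into line with Section 10.0.

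A third reply is that the identification aim is not left without data. This stands. Section 1.0 says that surgeons send frozen sections when in doubt about a tissue, and Sections 2.0 and 3.0 treat fewer frozen sections as an expected benefit. Items (iii) and (iv) are collected in both arms. A reader might infer that aim (i) has no both-arm measure; the documents do not support that. It has partial ones, but they are not the variable on which the trial was sized.

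**Conclusion.** The point holds as an omission between Sections 6.0 and 10.0. The variable behind the sample size is not listed for both-arm collection and comparison, and no common rule for counting it is given. As written, the plan cannot test the hypothesis it was sized for. It should be corrected before data collection, because glands left in place cannot be reliably counted later. The conclusion rests on the text reviewed and on reading the numbered list in Section 6.0 as the set of items to be compared, which is what its closing sentence says.

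Two stronger readings are tempting and should not be drawn. First, Section 6.0 describes the control surgeon as "relying solely on her/his surgical experience in identifying the parathyroid glands during the operations", whereas a detection ratio above 1.2 can inform the surgeon in the study arm. A reader might take this as evidence that glands are counted differently by arm. It is not: device against experience is the randomised contrast itself. What can be said is that no common counting rule is stated. Second, a reader might attach a bias or a false-positive rate to the gap. The documents give no figure for miscounting in either arm, so any such rate would rest on an invented shortfall. The effect on the result is therefore left unquantified.

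**What to change.** In Section 6.0, add an item to the list, for example: *(viii) number of distinct parathyroid glands identified per patient, recorded by the operating surgeon at the end of the procedure on the same form and by the same criterion in both arms (for example, a gland the surgeon declares to be parathyroid by the end of the operation), with histology of excised tissue as a supporting check.* In Section 10.0, state that this count is the outcome the sample size refers to.

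The cost is one extra field on a common operative form, an agreed definition and a sentence or two of text. The number of patients does not change. Two limits remain: the surgeon who records the count knows the arm, so it is unblinded, and histology can check only the glands that were removed.

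### About nine outcomes are compared with no primary outcome, alpha or error control, and the one outcome the trial is sized on is not among them

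*Combined protocol and SAP*

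**What the plan says.** Section 2.0 frames the question as a verdict on the device in three domains. The aim "is to determine if PTeye is beneficial or not for (i) intraoperative identification of parathyroid tissues", and likewise for surgical efficiency and for postsurgical complications.

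Section 6.0 lists what will be collected after demographics: "ii) duration of surgery, (iii) number of frozen section analysis performed, (iv) frozen section and permanent histology reports of all excised tissues"; calcium before surgery and at two later times; "parathyroid hormone (PTH) levels (5-14 days after surgery and 6 months after surgery"); and "postsurgical complications, if any and history of ER visits or hospitalization or repeat surgeries due to high calcium". It then gives the only comparison rule in the document: "These parameters would then be compared between the study arm and the control arm to truly gauge the impact or value of a device" of this kind.

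Section 10.0 is a single sample-size paragraph. It takes the mean number of parathyroid glands identified as its outcome, with an expected difference of 0.7 and SD of 1.0, and arrives at 33 per group, then 40 after attrition. It adds: "In order to detect a difference among individual surgeons, this will require recruitment of 40 patients per arm, per surgeon", for a total of 160.

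No section names a primary outcome, states an alpha, describes an analysis method, orders the comparisons or adjusts for their number.

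**The concern.** The outcome the trial was sized to detect is not among the comparisons listed, and none of the listed comparisons was sized. Section 6.0 sets several outcomes side by side with equal standing. If one reaches nominal significance, nothing in the plan tells a reader whether it was the hypothesis under test or one of many looks. A conclusion that PTeye is beneficial, or is not, would then carry no known error rate. Because no outcome is designated in advance, emphasis could also settle on whichever result turned out best, and the plan would offer no ground for objecting.

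**Working it through.** **1. The plan's own figure.** The documents give no overall type I error to reproduce. Their one calculated figure is 33 per group. With n = 2(z_alpha + z_power)² × (SD/difference)², difference 0.7 and SD 1.0:
- Two-sided 0.05, 80% power: 2 × (1.960 + 0.842)² / 0.49 = 32.04, rounded up to 33.
- Two-sided 0.05, 95% power: 2 × (1.960 + 1.645)² / 0.49 = 53.0, rounded up to 54.

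So 33 matches 80% power at two-sided 0.05, not the stated 95%. That is a separate matter. It is consistent with the per-test level assumed below, which the documents never state.

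**2. Count of comparisons (Section 6.0).** Duration 1, frozen-section count 1, histology results 1, calcium at two postoperative times 2, PTH at two times 2, complications 1, and ER visits/hospitalization/repeat surgery as a group 1: total 9. Leaving out histology and counting repeat surgery separately also gives 9. Counting calcium and PTH once each gives 7. Splitting the three healthcare events and adding glands identified gives 12.

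**3. Chance of at least one p<0.05 with no device effect, independent tests:** 1 − 0.95^k.
- k = 7: 30%
- k = 9: 37%
- k = 12: 46%

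**4. Allowing for correlation.** Simulation with equicorrelated normal test statistics, nine outcomes, two-sided 0.05. The benefit-only column counts significant results in the favourable direction.

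| Correlation | Either direction | False benefit only |
|---|---|---|
| 0 | 37% | 20% |
| 0.3 | 33% | 16.5% |
| 0.5 | 27% | 13.5% |
| 0.9 | 12% | 6% |

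For the independent case the benefit-only figure follows directly: 1 − 0.975^9 = 20.4%.

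**5. Rare binary outcomes.** Complications and healthcare events may be rare, and an exact test then rejects less often than 5%. Assuming Fisher's exact test, 80 per arm and event rates of 2% to 5% (rates not in the documents), its true size is 0.2% to 1.6%. With two such outcomes among the nine, the independent figure is 1 − 0.95^7 × (1 − size)², or 30% to 32%. With three it is 1 − 0.95^6 × (1 − size)³, or 27% to 30%.

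**6. By surgeon.** The total of 160 at 80 per surgeon implies two surgeons (160/80 = 2). The by-surgeon sentence belongs to the calculation for glands identified. Testing that one outcome overall and within each of two equal surgeon strata at 0.05 gives about 11.5% by simulation, with the overall statistic equal to (z1 + z2)/√2.

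**7. With one primary outcome tested once overall,** the rate is 5%.

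**The case against.** The best defence is that an outcome used alone for sizing is commonly read as the implicit primary. That has force, and it is why glands identified is the natural candidate. It does not settle the matter, because Section 10.0 never calls it primary and Section 6.0 does not list it for collection or comparison.

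A reader might infer that the plan lets any one significant result stand as proof of benefit. It does not say so. Section 6.0 says only that the parameters will be compared, and Section 2.0 asks about three domains rather than one omnibus question. The plan is silent, and so does not prevent selective claims; it does not prescribe an any-one-wins rule.

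A reader might also infer that all nine outcomes will be tested within each surgeon as well as overall, which would put the error at about 52% to 67% for correlations of 0.5 down to 0. The documents do not support that extension: the only by-surgeon sentence concerns the sized outcome.

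Two further points stand. The either-direction figures count apparent harm as well as benefit, so the benefit-only column is the one to set against a claim of benefit. The count of nine depends on how items are grouped, although 7 to 12 independent outcomes give 30% to 46%, so the conclusion does not turn on it.

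**Conclusion.** The concern holds in this form: the plan compares about nine outcomes to judge the device, designates none as primary, sets no error control, and omits its one powered outcome from the listed comparisons. With no device effect, the chance of at least one nominally significant overall result is 12% to 37% in either direction, or about 6% to 20% for a false benefit, over correlations from 0.9 to 0. For the sized outcome alone, adding by-surgeon tests gives about 11.5%.

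These figures assume two-sided 0.05 per test, nine tests with a common correlation, and (for the last) two equal surgeon strata. Exact testing of rare events would lower the nine-outcome figures somewhat. The trial can run as designed, but its conclusion about benefit would have no controlled error rate. The plan should be amended.

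**What to change.** Before outcome data are seen:
- Add the number of parathyroid glands identified to the Section 6.0 data list for both arms. State who counts a gland and how it is confirmed, in the same way in each arm.
- Name it the single primary outcome in Section 10.0. Test it once at two-sided 5% over all surgeons, with surgeon in the model.
- Report by-surgeon results and all other outcomes as secondary, with confidence intervals. Make no confirmatory claim of benefit from a lone secondary result unless a fixed order or Holm's procedure is prespecified.

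If the sponsor regards another outcome as the real question, that outcome can be named instead, but the sample size must then be justified for it.

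The cost is a short amendment and one additional data item. No extra patients are needed: at 80 per arm, a difference of 0.7 with SD 1.0 has about 99% power at two-sided 0.05. The downside is that a lone significant secondary result could no longer be claimed as proof of benefit.

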## **7.0 Risks**

- The proposed study is designed to collect NIRAF measurements from neck tissues with a commercial device called PTeye during a parathyroidectomy.
- Each PTeye measurement takes less than 2 seconds, with the whole set of measurements not adding more than 5 minutes to the surgical procedure. Thus, there is a minimal increase of risk of surgery due to the potential five extra minutes of anesthesia time associated with the study. In addition, the participating surgeon will evaluate the eligibility of the patient based on his or her medical condition. Patients with high anesthetic risks will not be asked to participate in the study.
- Since the power of near infrared light from PTeye will be extremely low, no side effects should be introduced to the patient.
- There should not be any discomforts, inconveniences, and/or risk resulting from this study.
- The study should not increase the risk of infection as a disposable sterile probe is used for each patient.
- The PTeye device used in this study has been granted clearance for marketing by the FDA. The marketing authorization by FDA has been granted based on the caveat that necessary precautionary measures will be taken by the surgeon to minimize the probable risks (as listed in the device brochure). The PTeye may be associated with unknown/unforeseen risks as with any other FDA-cleared medical devices used during surgical procedures.

## **8.0 Reporting of Adverse Events or Unanticipated Problems involving Risk to Participants or Others**

Upon identification, adverse events resulting from this *in vivo* data acquisition procedure will be reported to the PI as well as the UM IRB immediately. The study will be immediately terminated and not resumed until the sources leading to the adverse events are identified.

## **9.0 Study Withdrawal/Discontinuation**

The data acquisition procedure will be terminated if the medical conditions of the participant show some unexpected and adverse changes. The decision of terminating the study will be determined by the participating surgeon.

## **10.0 Statistical Considerations**

Benmiloud *et al.* studied the impact of NIRAF-based identification of parathyroid glands which comprised of a group of 93 patients where NIRAF was used by a surgeon for parathyroid identification and a control group of 153 patients where NIRAF was not used (19). Their study reported that mean parathyroid glands identified by surgeon with NIRAF imaging was significantly higher at  $3.1 \pm 0.9$ , while that of same surgeon without NIRAF imaging was  $2.6 \pm 0.1$  ( $p=0.0001$ ). Based on this data (mean difference: 0.5 and standard deviation: 1.0), it was determined that in order to observe a statistically significant difference (i.e. for an expected mean difference: 0.7 and expected standard deviation: 1.0), 33 patients would be required per group (for a 95% powered study). Since this study may involve patient follow-up for data up to 6 months after surgery, we will thus assume an approximate data attrition rate of 20%, thus requiring a recruitment of 40 patients per group. In order to detect a difference among individual surgeons, this will require recruitment of 40 patients per arm, per surgeon. Therefore, a total of 160 patients (study and control arm) should be recruited for this study at this study site.

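### Section 10.0 claims 95% power for 33 patients per group, but its own inputs give about 80% (two-sided 5%) or 88% (one-sided 5%)

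*Combined protocol and SAP*

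**What the plan says.** Section 10.0 is the only place where the plan gives a power figure. It starts from a published before-and-after comparison of the number of parathyroid glands identified and summarises it thus: "Based on this data (mean difference: 0.5 and standard deviation: 1.0". The calculation itself uses a larger effect, "for an expected mean difference: 0.7 and expected standard deviation: 1.0", and the result is that "33 patients would be required per group (for a 95% powered study".

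The section then allows for loss to follow-up: "we will thus assume an approximate data attrition rate of 20%, thus requiring a recruitment of 40 patients per group". Finally it multiplies up: "In order to detect a difference among individual surgeons, this will require recruitment of 40 patients per arm, per surgeon". The stated total is 160, which implies two surgeons, because 160 / (2 × 40) = 2.

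No significance level, sidedness or test is named. The nearest wording is that the size was chosen "in order to observe a statistically significant difference".

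**The concern.** A standardised difference of 0.7 (0.7 / 1.0) with 33 per group is the familiar answer for 80% power at two-sided 5%, so the 95% label looked wrong at once. The gap is material: 95% power means a 5% chance of missing a true difference of 0.7, whereas 80% means a 20% chance.

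Every later sample-size figure in the plan is built on this one. The total is assembled from a per-surgeon requirement, so the within-surgeon comparison is where the error applies. A null result within one surgeon could be presented as coming from a 95% powered comparison when it did not.

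**Working it through.** **Inputs from Section 10.0:** difference δ = 0.7; common SD σ = 1.0; two equal groups; n = 33 per group; stated power 95%.

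**Assumed, because not stated:** two-sample comparison of means, two-sided alpha 0.05. One-sided 0.05 is shown as well.

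**Step 1. Try to reproduce 33 per group.** Normal approximation: n = 2σ²(z_alpha + z_power)² / δ².

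- 95% power, two-sided 5%: 2 × (1.960 + 1.645)² / 0.49 = 53.0, so 54. The t test gives 54.02, so 55.
- 95% power, one-sided 5%: 2 × (1.645 + 1.645)² / 0.49 = 44.2, so 45. The t test gives 44.87, so 45.
- 80% power, two-sided 5%: 2 × (1.960 + 0.842)² / 0.49 = 32.04, so **33**. The t test gives 33.02.

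The plan's 33 matches 80% power, not 95%.

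**Step 2. Power of 33 per group.** SE = √(2/33) = 0.246, and 0.7 / 0.246 = 2.843.

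- Two-sided 5%: Φ(2.843 − 1.960) = 81.2%; t test 80.0%.
- One-sided 5%: Φ(2.843 − 1.645) = 88.5%; t test 87.9%.

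**Step 3. What would make 95% true at n = 33?** Changing one input at a time (t test): a two-sided alpha of 0.237, or a difference of 0.90, or an SD of 0.78. Even one-sided 10%, which the plan does not mention, gives 93.9%.

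**Step 4. Power at the sizes the plan would deliver** (t test, two-sided 5%, SD 1.0). The attrition allowance leaves 40 × 0.8 = 32, one short of the plan's own 33. Dividing properly, 33 / 0.8 = 41.25, so 42; the plan's 40 is 33 × 1.2 = 39.6, rounded up.

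| Comparison | n per arm | Power at 0.7 | Power at 0.5 |
|---|---|---|---|
| One surgeon, 20% lost | 32 | 78.7% | – |
| One surgeon, plan's evaluable n | 33 | 80.0% | 51.6% |
| One surgeon, none lost | 40 | 87.1% | 59.8% |
| Two surgeons pooled, 20% lost | 64 | 97.6% | 80.2% |
| Two surgeons pooled, none lost | 80 | 99.3% | 88.2% |

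At one-sided 5% and a difference of 0.7, 40 per arm gives 92.8%. No size from 32 to 40 per arm reaches 95% under either convention.

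**Step 5. The other reading of the surgeon sentence.** If the aim is to detect a device effect that differs by 0.7 between the two surgeons, the contrast has SE = √(4/n), with n per surgeon-by-arm cell (normal approximation, two-sided 5%).

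- n = 32: SE = 0.354; Φ(0.7/0.354 − 1.960) = 50.8%.
- n = 40: SE = 0.316; Φ(0.7/0.316 − 1.960) = 60.0%.

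**The case against.** The strongest reply is that the comparison that matters is the pooled one. Section 6.0 compares the study arm with the control arm and describes no within-surgeon analysis. Pooled power at 0.7 exceeds 95%. That stands, and it limits the consequence. It does not make the sentence true, because Section 10.0 attaches 95% to 33 per group and then sets recruitment per surgeon on that basis.

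Second, the lower within-surgeon figure may be too pessimistic. The attrition allowance is for follow-up to six months, whereas glands are identified during the operation, when "the surgeon will use the PTeye as an intraoperative tool to identify if a suspect tissue is a parathyroid or not". If no gland counts are lost, all 40 per arm contribute and power is 87.1%. That is fair, and it is why a range is given, but 87.1% is still not 95%.

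Third, the error may lie in the inputs and not in the power label. Pooling the SDs quoted from the cited study (0.9 with 93 patients, 0.1 with 153) gives √[(92 × 0.81 + 152 × 0.01) / 244] = 0.56. With a difference of 0.5, the normal formula then gives 33 per group for 95% power. The match may be chance: the plan states an SD of 1.0 twice and ties its 33 to 0.7. If that route was used, the stated inputs are wrong and the sentence still needs correcting. The documents cannot show which element is at fault, so the sponsor should be asked.

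Finally, optimism about the effect (0.7 against 0.5) and the surgeon-by-arm contrast are not part of the arithmetic error. They matter only for how a corrected statement is worded.

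**Conclusion.** The concern holds. On the plan's own difference and SD, 33 per group gives about 80% power at two-sided 5% and about 88% at one-sided 5%. The type II error is therefore about 20% or 12%, against the 5% claimed. No conventional alpha gives 95%.

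The conclusion assumes a two-sample comparison of means with equal arms. The alpha is also an assumption, but the result does not depend on choosing between the usual conventions. That 95% is a confidence level entered as power is plausible, but it is an inference and nothing here rests on it.

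The error affects the per-surgeon calculation. The pooled comparison keeps more than 95% power at 0.7, but not at 0.5. Because this is the plan's only power figure and the basis of its recruitment target, it should be corrected.

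**What to change.** First confirm with the sponsor which element is wrong: the power, the alpha or the inputs. Then amend Section 10.0:

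- State alpha, sidedness and the test.
- If the inputs stand, replace the power claim with wording such as: *33 evaluable patients per group give about 80% power (two-sample t test, two-sided alpha 0.05) for a mean difference of 0.7 with SD 1.0.* If another alpha or test was meant, give the matching figure.
- For PTeye against control within one surgeon, give about 79% (32 evaluable per arm) to 87% (all 40 evaluable). Do not say that recruiting 40 secures 33 after a 20% loss.
- If a pooled figure is added, tie it to the difference: about 98% to 99% at 0.7 and 80% to 88% at 0.5, with 64 to 80 per arm.
- Say what a difference among surgeons means. If it means a device effect that differs by 0.7 between two surgeons, report power of about 51% to 60%.

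**Cost:** wording only, with no extra patients, if about 79% to 87% within each surgeon is acceptable. If 95% within each surgeon was intended, that is a design decision. At two-sided 5% it needs 55 evaluable per arm per surgeon, or 55 × 4 = 220 for two surgeons. With 20% loss, 55 / 0.8 = 68.75, so 69 per arm per surgeon and 69 × 4 = 276 recruited, against the planned 160.

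### Recruiting 40 per group leaves 32 after the assumed 20% attrition, one short of the 33 required: a small slip in each surgeon-by-arm cell

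*Combined protocol and SAP*

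**What the plan says.** The whole sample size argument is one paragraph in section 10.0, Statistical Considerations. It takes the number of parathyroid glands identified as the sizing outcome, with assumptions given as "for an expected mean difference: 0.7 and expected standard deviation: 1.0", and concludes that "33 patients would be required per group". It then allows for loss, giving follow-up to 6 months as the reason: "we will thus assume an approximate data attrition rate of 20%, thus requiring a recruitment of 40 patients per group".

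The 40 is next applied to each arm for each surgeon, and the paragraph ends with "a total of 160 patients (study and control arm) should be recruited for this study at this study site". With 40 per arm and two arms, 160 implies two surgeons, although that number is not stated. No inflation formula is shown. No other section gives a different attrition rate or a larger target.

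**The concern.** An attrition allowance should return the required number of evaluable patients once the expected loss has occurred, so the required number is divided by the fraction retained. Here the allowance appears to have been added on as a percentage of 33, which always undershoots. The recruitment target then falls short of the plan's own requirement at the plan's own loss rate. The figure is carried into every surgeon-by-arm cell and into the total of 160.

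The reason given for the allowance also fits poorly. Loss over 6 months bears on the late calcium, PTH and complication data listed in section 6.0. The outcome used for sizing is a count made during the operation. At stake is whether a reader can tell how many evaluable patients the plan expects, and for which outcome.

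**Working it through.** **Inputs, all from section 10.0 unless marked**
- Required per group: 33
- Attrition: 20%, described as approximate
- Recruited per group: 40, applied per arm per surgeon; total 160
- Difference 0.7, SD 1.0
- Significance level and sidedness: not stated; two-sided 5% assumed

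**Step 1. Reproduce the plan's 40.**
Adding the allowance on: 33 × (1 + 0.20) = 39.6, rounded up to 40. This matches exactly. Because no formula is shown, that route is an inference, but the steps below do not depend on it.

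**Step 2. Apply the stated loss to the stated target.**
40 × (1 − 0.20) = 32, against 33 required.

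**Step 3. Divide the loss out.**
33 / (1 − 0.20) = 41.25, rounded up to 42 per arm per surgeon. With two arms and two surgeons, 4 × 42 = 168, against 160. The difference is 8 patients, or 8/160 = 5%.

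**Step 4. Find the loss that 40 covers.**
1 − 33/40 = 17.5%.

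**Step 5. Cost in power within one surgeon** (two-sample t-test, standardised difference 0.7/1.0 = 0.7, two-sided 5%)

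| Evaluable per arm | Power |
|---|---|
| 32 | 78.7% |
| 33 | 80.0% |

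The drop is 1.3 points. The normal approximation gives 80.0% and 81.2%, a drop of 1.2 points.

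**Step 6. The pooled comparison.**
Two surgeons at 40 give 80 per arm; 80 × 0.8 = 64. Power with 64 per arm is about 97.6% under the same assumptions, ignoring any surgeon effect.

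**Step 7. Check the base of 33.**
With the normal approximation, 33 per group is the answer for 80% power at two-sided 5%. For the 95% that the plan states, the base would be 54 (normal approximation) or 55 (t-test). Dividing out 20% gives 54/0.8 = 67.5, so 68, or 55/0.8 = 68.75, so 69. This is a separate discrepancy. It is shown here only because the attrition step takes the base as given.

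**The case against.** The best defence is that nothing of substance is lost. The rate is called approximate, 40 covers 17.5%, and the gap is one patient per cell. The 33 was derived only for the gland count, which is made at surgery. If 6-month loss does not touch that count, up to 40 per cell are available, which is more than 33. The plan sets no required number for the 6-month outcomes, so 32 is not below any requirement stated for them.

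Most of this stands, and it limits the point. It does not remove it: the approximation belongs to the rate and not to the arithmetic, and at the only rate given, 40 does not return 33.

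Three stronger readings are tempting, and the documents do not support them.
- A reader might infer that the trial as a whole is underpowered by this slip. The shortfall exists only within a surgeon; the pooled comparison keeps about 64 per arm.
- A reader might infer that the plan gives no usable evaluable number for any outcome. For the gland count, 33 required and 40 recruited are compatible if 6-month loss does not apply to it.
- A reader might infer that the sponsor can simply promise a gland count on all 40. Section 6.0's list of data to be compiled does not name the number of glands identified, and section 9.0 allows data acquisition to be terminated for a participant. Lower loss at surgery is a reasonable expectation, but complete data are not assured.

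**Conclusion.** The attrition step is wrong as written. At a 20% loss, 40 per group yields 32 and not 33; the number that keeps 33 is 42. The effect is one evaluable patient and about 1.3 points of power in each surgeon-by-arm cell, assuming a difference of 0.7, SD 1.0, a two-sided 5% t-test, and the 20% loss applied literally to the sizing outcome. If loss on the gland count is 17.5% or less, there is no shortfall for that outcome.

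The gap between the stated 95% power and the roughly 80% that 33 per group provides is much larger, but this slip does not cause it and correcting the slip will not close it.

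**What to change.** Correct the attrition sentence in section 10.0 and leave recruitment as it is.
- Keep 40 per arm per surgeon and 160 in total. State that 40 covers a loss of up to 17.5% against a requirement of 33, and that a 20% loss would leave 32 evaluable per cell.
- State that the allowance concerns the 6-month outcomes, and that less loss is expected for the gland count made at surgery.
- If the intention is to retain 33 after a 20% loss, change the figures to 42 per arm per surgeon and 168 in total.
- If the base of 33 is revised when the power statement is settled, redo the division by 0.8 on the new base.

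The first course costs one or two sentences and no extra patients, and the stated attrition cover becomes slightly less favourable (17.5% in place of 20%). The alternative costs 8 more patients, 5% of the present total.
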